9.11 HIV Incidence

HIV incidence rate will be calculated as the total number of participants with confirmed HIV infection during study follow-up divided by the person-years accumulated in each arm. 95% CIs will be calculated based on Poisson distribution assumptions. In addition, exact tests based on the Poisson distribution will be used to compare HIV incidence rate between the treatment arms.

9.12 Evaluate the Safety, Tolerability and Pharmacokinetics of 744LA in the Women Who Use Injectable Hormonal Contraception

The safety and tolerability analyses described above will be performed on the subset of female participants who self-report the use of injectable hormonal-based contraception at study entry or at any time during the study period. Proportions of such women meeting safety or tolerability endpoints will be compared a) across treatment arms b) to the women in the 744LA arm who are do not report use of injectable hormonal contraception c) to the overall study population randomized to active GSK1265744. The comparisons in a) are to evaluate the safety and tolerability of the 744LA injection in the women who report use of injectable hormonal-based contraception between the two treatment arms. The comparisons in b) are to evaluate the safety and tolerability of the 744LA injection between the women who report the use of injectable hormonal-based contraception and the women who are do not report the use of injectable hormonal-based contraception. The comparisons in c) are to evaluate the safety and tolerability of the women who report the use of injectable hormonal-based contraception in contrast to the rest of the enrolled participants in the study. All comparisons will be done using the Fisher exact test. The data will be analyzed by cohort and in aggregate.

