2.4 Schema

Cohort 1

W = Week

Cohort 2

The 110 participants in Cohort 1 and 90 participants in Cohort 2 were randomized to one of the two study arms with an active GSK 744 to placebo ratio of 3:1, stratified by gender and region (US and non US), as follows:

Cohort 1

Arm 1: 82 participants received daily oral 744 (30 mg tablets) for 4 weeks, followed by an one week washout period, to establish safety and tolerability, followed by intra-muscular (IM) gluteal injections of 800 mg of 744LA (administered as two sequential 400 mg gluteal injections) at three time points at 12 week intervals as: Week 5, Week 17, and Week 29.

Arm 2: 28 participants received daily oral matching placebo and IM injections of vehicle-matched placebo on the same schedule as Arm 1.

Cohort 2

Arm 1: Approximately 66 participants will receive daily oral 744 (30 mg tablets) for 4 weeks, followed by a one week washout period, to establish safety and tolerability, followed by intra-muscular (IM) gluteal injections of 600 mg of 744LA (administered as one 600 mg gluteal injection) at five time points at 4 and 8 week intervals as: Week 5, Week 9, Week 17, Week 25, and Week 33.

Arm 2: Approximately 22 participants will receive daily oral matching placebo and IM injections of vehicle-matched placebo on the same schedule as Arm 1.

All participants will receive HIV testing with pre- and post-test counseling, in addition to risk-reduction counseling and condoms and lubricant. All participants will be followed according to the Schedule of Evaluations and Procedures provided in HPTN077 protocol Appendices I-IV.

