4.3 Study Duration

Approximately 3 years. Accrual will require approximately 16 to 24 weeks (4 – 6 months) for each cohort. Study participants in both cohorts will receive oral tablets for 4 weeks, followed by a 1 week wash out period. Cohort 1 will then receive intra-muscular injections at 3 time points over 24 weeks (6 months); cohort 2 will receive intra-muscular injections at five time points over 28 weeks (7 months). Participants in the active study product arm will be followed for 76 weeks (18 months) after their last injection. Participants in the placebo arm will be followed until 76 weeks after their last injection or until the last participant in the active study product arm in cohort 2 completes their Week 41 visit, whichever comes first, at which time the study will be unblinded to assess the primary endpoint. When all procedures related to unblinding are completed, participants in the placebo arm will no longer be followed.

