7 ASSESSMENT WINDOWS

7.1 Treatment Periods

Adverse events, laboratory, vital signs and liver events will be assessed and denoted within the treatment periods that are defined below.

Oral Phase is defined as the time between the enrollment date (Week 0) and the day of the 1st injection (Week 5) or the day of withdrawal, whichever comes first.

Injection Phase is defined as the time between the first injection and the 12 weeks visit after the last injection. For the participants who complete all three injections, the injection phase assessment window is the time between Week 5 and Week 41 visits. For the participants who complete the two injections, the injection phase assessment window is the time between Week 5 visit and Week 29 visit. For the participants who complete only the first injection, the injection phase assessment window is the time between Week 5 visit and Week 17 visit.

Tail Phase is defined as the time between Week 41 to Week 105/109 for ITT analysis. However, for per protocol analysis such as pharmacokinetics analysis, for the participants who did not complete full injections (3 injections for cohort 1 and 5 injections for cohort 2), the tail phase assessment window starts at the 12th (the 8th) weeks after the last injection for cohort 1 (cohort 2) to the last follow-up visit.

On-Treatment is defined as the time between the beginning of the oral phase and the end of the follow-up phase (from the participants' enrollment day to the participants' last day subject's last day in the study).

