11.3 Pharmacokinetic and Other Secondary Analyses

11.3.1 List of Tables

Table 21 Summary of pharmacokinetic parameters by injection

Table 22 Assess the time to steady state of the plasma drug concentration, C_{τ}

Table 23 Associations of sex at birth (or BMI) with pharmacokinetic parameters

Table 24 Change in sexual risk behavior (number of sexual partners) from baseline

Table 25 HIV incidences during the study

Table 26 Reported pregnancies by treatment arm and cohort

Table 27 The proportion of women experiencing any Grade 2 or higher AEs (a) prior to completion of the full oral phase and (b) prior to completion of the full injection phase --- among the women who use any injectable hormonal contraception (combined cohort)

Table 28 The proportion of the women who discontinue the study product for reasons of toxicity, tolerability, or acceptability (a) prior to completion of the full oral phase and (b) prior to completion of the full injection phase—among the women who use any injectable hormonal contraception

Table 29 Summary of pharmacokinetic parameters by injection and cohort —among the women who use any injectable hormonal contraception

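### The HIV incidence test compares whole-follow-up rates, although 26% to 46% of planned active-arm time has no concurrent placebo follow-up

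*SAP*

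**What the plan says.** Section 9.11 sets one rate per arm over all follow-up: participants with "confirmed HIV infection during study follow-up divided by the person-years accumulated in each arm". It adds that "exact tests based on the Poisson distribution will be used to compare HIV incidence rate between the treatment arms". The planned output, Table 25, is titled "HIV incidences during the study". Neither the section nor the title mentions phase.

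Follow-up differs by arm. Under Section 4.3, active participants are followed for 76 weeks after their last injection. Placebo participants stop at the earlier of 76 weeks after their last injection and the last active Cohort 2 participant's Week 41 visit. The section closes: "When all procedures related to unblinding are completed, participants in the placebo arm will no longer be followed". Section 4.8 gives 52 weeks, not 76, for active follow-up after unblinding.

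Section 7.1 does define phases: "Tail Phase is defined as the time between Week 41 to Week 105/109 for ITT analysis". Other analyses use them. Table 19 splits Grade 2 or higher events into oral, injection, tail and on-treatment periods. Section 9.10 compares behaviour between arms at Week 5 and then within the injection phase.

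**The concern.** Dividing by person-years corrects for unequal length of follow-up. It does not correct for unequal composition. The active rate includes a block of later, unblinded time that the placebo rate cannot include. With no drug effect, the exact Poisson test is valid only if background incidence is the same in that block as before it. The SAP neither states nor checks this, and risk behaviour after unblinding or calendar trends in exposure could break it.

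A second issue is separate. Even with full placebo follow-up, one pooled rate would mix time on injections with time long after the last one. An infection a year after the last dose would count the same as one during dosing.

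A small number of infections could then be read as a treatment difference, or as its absence, without regard to when they occurred.

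**Working it through.** **Inputs from the SAP.** Section 2.4 gives an "active GSK 744 to placebo ratio of 3:1". For Cohort 1: "Arm 1: 82 participants received daily oral 744" and "Arm 2: 28 participants received daily oral matching placebo". Cohort 2 has about 66 active and 22 placebo. These sum to 88 against the stated 90, which has negligible effect here. Section 4.3 gives accrual of 16 to 24 weeks per cohort and a total duration of about 3 years. The last injections are at Weeks 29 and 33.

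**Plan's own figures.** Final visits are 29 + 76 = 105 and 33 + 76 = 109. Both match Section 4.4.

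**Active person-time, no dropout.**
- Total: 82 × 105 + 66 × 109 = 15,804 weeks = 303.9 PY.
- To Week 41: 148 × 41 = 6,068 weeks = 116.7 PY.
- After Week 41: 9,736 weeks = 187.2 PY, or 62%.
- With 52 weeks of follow-up: 82 × 81 + 66 × 85 = 12,252 weeks = 235.6 PY, of which 118.9 PY (50%) is after Week 41.

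**Placebo to Week 41.** 50 × 41/52 = 39.4 PY, so the ratio is 2.96:1, in line with randomisation.

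**Time before and after the cut-off.** The SAP gives no Cohort 2 start date. I assume uniform accrual over A weeks in each cohort, Cohort 2 opening g weeks after Cohort 1 closes, and unblinding at the last Cohort 2 Week 41 visit. The cut-off is then 2A + g + 41 weeks after the study opens. Each participant's follow-up is capped at Week 105 or 109. Mean follow-up to the cut-off is:
- Cohort 2: 41 + A/2.
- Cohort 1: 41 + 1.5A + g where nobody reaches the cap.
- Cohort 1 with A = 24, g = 26 (cut-off 115): those entering in the first 10 weeks reach 105, so the mean is (10/24) × 105 + (14/24) × 98 = 100.9.

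Non-concurrent active weeks = 82 × (105 − Cohort 1 mean) + 66 × (109 − Cohort 2 mean).

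| A, g | Means (C1, C2) | Non-concurrent active PY | Share of 303.9 | Placebo tail PY | Total placebo PY |
|---|---|---|---|---|---|
| 16, 0 | 65, 49 | 7,240/52 = 139.2 | 46% | 848/52 = 16.3 | 55.7 |
| 24, 0 | 77, 53 | 5,992/52 = 115.2 | 38% | 1,272/52 = 24.5 | 63.9 |
| 16, 26 | 91, 49 | 5,108/52 = 98.2 | 32% | 1,576/52 = 30.3 | 69.7 |
| 24, 26 | 100.9, 53 | 4,031/52 = 77.5 | 26% | 1,942/52 = 37.3 | 76.8 |

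Total durations (2A + g + 109) are 141, 157, 167 and 183 weeks. The second row is closest to 3 years (156 weeks).

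On the 52-week reading, the first row becomes [82 × (81 − 65) + 66 × (85 − 49)]/52 = 70.9 PY (30% of 235.6). In the last row all of Cohort 1 finishes before the cut-off, so it becomes 66 × (85 − 53)/52 = 40.6 PY (17%).

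**Effect with no drug effect.** If incidence is multiplied by k after unblinding, and s is the non-concurrent share, the pooled ratio is 1 + s(k − 1).
- k = 2: 1.26 (s = 0.255) to 1.46 (s = 0.458).
- k = 0.5: 0.87 to 0.77.
- k = 1: 1.00.

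**Mixing of dosing and post-dosing time.** Take a ratio of 0.2 while protected, 1.0 afterwards, and a constant background rate. If protection lasts x weeks beyond Week 41, protected time is 148 × (41 + x)/52 and the pooled ratio is 1 − 0.8 × protected PY/303.9.

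| x (weeks) | Protected PY | Pooled ratio |
|---|---|---|
| 0 | 116.7 | 0.69 |
| 12 | 150.8 | 0.60 |
| 26 | 190.7 | 0.50 |
| 52 | 264.7 | 0.30 |

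These ratios use active-arm time only, so they would be the same with full placebo follow-up.

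**The case against.** The best defence is that Section 3.2 defines the endpoint as a count of infections over the whole study period, so tail infections are meant to count. Section 9.11 never claims to estimate efficacy while dosed. Participants are at low to minimal risk. At an assumed 0.1 to 1 infection per 100 PY, 56 to 77 placebo PY would yield about 0.06 to 0.8 infections, so no analysis will estimate a ratio well. The Table 25 shell is not shown and might contain a phase split. Section 9.13 allows exploration of PK against HIV conversion, though only as an option.

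Much of this stands. It justifies keeping the whole-study count and limits the practical weight of the point. It does not justify a prespecified between-arm test on time that is partly non-concurrent.

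A reader might go further and infer that the plan counts infections after coverage ends against 744LA with almost no placebo time to set against them. The SAP does not support that:
- It does not say when protection ends, and Week 41 is only one dosing interval after the last injection.
- Placebo tail time is 16 to 37 PY, and about 48 to 110 PY of the active tail (187.2 minus 139.2 or 77.5) runs alongside it.
- Bias from the missing placebo time can go either way, and is absent if background incidence is constant.

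**Conclusion.** The point holds as a cheap improvement to a secondary analysis. No primary endpoint is affected.

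By design, about 26% to 46% of active person-time (17% to 30% if active follow-up is 52 weeks) has no concurrent placebo time. The between-arm ratio is then biased whenever background incidence changes over time or with unblinding. The ranges rest on uniform accrual, an assumed Cohort 2 start, no dropout and no lag before unblinding. A lag would add placebo tail time and shrink the gap. The doubling and halving of incidence are illustrations, not forecasts.

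Separately, 62% of active time (about 50% on the 52-week reading) is after Week 41, so the pooled rate does not isolate incidence during dosing. The size of any dilution cannot be fixed from the SAP, because it depends on when protection ends.

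**What to change.** In Section 9.11 and Table 25:

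- Restrict the between-arm exact Poisson comparison to blinded, concurrent follow-up by censoring both arms at the calendar date of unblinding. Stratify by time to Week 41 and tail, or show the two separately. A cut at Week 41 alone would discard blinded, randomised tail time, mainly from Cohort 1.
- Report infections, person-years and exact Poisson 95% CIs by arm for the oral, injection and tail phases. State the phase boundary for early discontinuers. Section 7.1 ends their injection window at Week 17 or 29 but starts the ITT tail at Week 41.
- Describe active-arm infections after unblinding individually, with time since last injection.
- Keep the whole-study count for the Section 3.2 endpoint.

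Reconcile the 76 weeks in Section 4.3 with the 52 weeks in Section 4.8, since the choice changes the active denominator from 303.9 to 235.6 PY.

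The cost is a few sentences and one table split, with no new data. The comparison loses the non-concurrent active time, so its interval widens. Under the assumptions above it keeps all placebo time and restores a ratio near the randomised one (for example, 303.9 − 139.2 = 164.7 PY against 55.7 PY, or 2.96:1).

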4 STUDY DESIGN

4.1 Participants

200 men and women at low to minimal risk for acquiring HIV infection, ages 18 to 65, randomized 3:1, with approximately 150 in the active drug arm, and 50 in the placebo arm. It is anticipated that approximately 60% of the enrolled participants will be women.

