4.7 Randomization

Enrolled participants are randomized to one of two study arms with an active GSK1265744 to placebo ratio of 3:1 in two cohorts. The arm randomization is stratified by

gender and region (US and non-US sites) and done in blocks to ensure balanced treatment assignments within each gender and region (US and non-US). The randomization scheme is generated, operationalized and maintained by HPTN SDMC using Frontier Science & Technology Research Foundation, Inc. (FSTRF) system. Additional details regarding the process of randomization are included in the SSP Manual.

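### SAP section 9.12, comparison (b): as worded, contraceptive users from both arms are set against non-users in the 744LA arm only, which mixes treatment into the contraceptive contrast

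*SAP*

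**What the plan says.** SAP section 9.12 specifies that the safety and tolerability analyses are "performed on the subset of female participants who self-report the use of injectable hormonal-based contraception at study entry or at any time during the study". This definition carries no restriction by arm.

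The next sentence has one subject for three comparisons. It begins "Proportions of such women meeting safety or tolerability endpoints will be compared a) across treatment arms", goes on "b) to the women in the 744LA arm who are do not report use of injectable hormonal contraception", and ends with (c), a comparison with everyone randomised to active drug.

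The section then explains each comparison. For (b) it says: "The comparisons in b) are to evaluate the safety and tolerability of the 744LA injection between the women who report the use" of injectable contraception and those who do not. This sentence names the 744LA injection as the object but limits neither group by arm.

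The method is fixed for all three: "All comparisons will be done using the Fisher exact test". No adjustment for or stratification by arm is given.

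On allocation, section 4.1 has participants "randomized 3:1, with approximately 150 in the active drug arm, and 50 in the placebo arm". Section 4.7 stratifies by "gender and region (US and non-US sites) and done in blocks to ensure balanced treatment assignments within each gender and region", so the 3:1 ratio is expected to hold among women.

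**The concern.** Comparison (a) can be carried out only if the user subset contains women on placebo. The same subset is then the first side of (b), whose second side is non-users on 744LA only. The two sides of (b) therefore differ in contraceptive use and also in treatment, and a Fisher test on the resulting two-by-two table cannot separate them.

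The question behind (b) is whether 744LA is less safe or less well tolerated in women who also use an injectable contraceptive. Placebo women on the user side can produce a difference where there is none, or shrink one that is there. If 744LA causes more events than placebo, the error runs towards reassurance.

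**Working it through.** **Plan's own figure.** The SAP gives no sample size, event rate or power for section 9.12, so there is nothing to reproduce. The allocation figures in section 2.4 agree with 3:1: 82/110 = 74.5% active in Cohort 1, and 66/(66+22) = 75% in Cohort 2.

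**Inputs from the SAP.**
- Users: all female users, both arms (section 9.12).
- Non-users in (b): 744LA arm only (section 9.12).
- Test: unadjusted Fisher exact (section 9.12).
- Allocation: 3:1, stratified by gender (sections 4.1 and 4.7).
- Women: about 60% of 200 = 120, so about 90 on 744LA and 30 on placebo (section 4.1).

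**Assumptions, because the SAP gives no figures.** Two-sided level 0.05; 36 users on 744LA, 12 users on placebo and 50 non-users on 744LA (86 women on 744LA, near the expected 90); the event rates below; and reporting of contraceptive use that does not depend on arm, so that users also split 3:1.

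**Step 1: bias.** The expected proportion among users as written is 0.75 x (rate in 744LA users) + 0.25 x (rate in placebo users). Compared with users on 744LA alone, the contrast is shifted by

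0.25 x (placebo rate minus 744LA rate, among users).

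The shift depends on the 3:1 split and not on how many women use contraception.

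**Step 2: no contraceptive effect, 80% on 744LA.**
- Placebo 60%: 0.75 x 80 + 0.25 x 60 = 75%, a difference of -5 points from the non-users.
- Placebo 50%: 0.75 x 80 + 0.25 x 50 = 72.5%, a difference of -7.5 points.

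Probability that Fisher's test rejects, by full enumeration of the binomial outcomes:

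| Placebo rate | Expected difference | As written | Users restricted to 744LA |
|---|---|---|---|
| 80% | 0 | 3.7% | 3.8% |
| 70% | -2.5 points | 4.6% | 3.8% |
| 60% | -5 points | 7.0% | 3.8% |
| 50% | -7.5 points | 11.0% | 3.8% |

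In the last row, 10.8 of the 11.0 percentage points are rejections in which users look safer.

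**Step 3: a true contraceptive difference, 70% in 744LA users and 50% in 744LA non-users.**

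| Placebo users' rate | Expected difference as written | Power as written | Power, users restricted to 744LA |
|---|---|---|---|
| 50% | 0.75 x 70 + 0.25 x 50 - 50 = +15 points | 31% | 43% |
| 30% | 0.75 x 70 + 0.25 x 30 - 50 = +10 points | 15% | 43% |

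**Step 4: rare events.** With 5% to 10% on 744LA and 0% on placebo, the shift is 0.25 x 5 = 1.25 to 0.25 x 10 = 2.5 points, which is small.

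**The case against.** The strongest reply is that this is loose wording and not a chosen analysis. The heading of section 9.12 concerns 744LA in contraceptive users, the explanatory sentence for (b) concerns the 744LA injection, and the comparator is explicitly in the 744LA arm. Placebo women received saline (section 2.3) and cannot inform that purpose. A reader might infer from the literal text that the sponsor means to pool the arms on the user side. The document does not support that inference, and the purpose sentence points the other way. What stands against the reply is that the restriction on users is written nowhere, while the sentence that a programmer would follow limits one side and leaves the other open.

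Second, little is lost for a careful reader. Comparison (a) will show the proportion among 744LA users separately, so the right point contrast could be put together by hand. Tables 27 to 29 in section 11.3.1 cover users only, and no listed output names a contrast of users with non-users. Both points are fair and limit the consequence. They do not make the specified test correct.

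Third, the size rests on assumed rates. This also stands. The bias is zero when the arms have equal rates, and in the illustration rejection stays below 5% up to a 10-point difference between arms. That users would look safer holds only if 744LA has more events than placebo, which the SAP does not state.

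**Conclusion.** The point holds as a defect in the specified comparison. As worded, (b) compares users from both arms with non-users from one arm, by a test that ignores arm, and so does not match its own stated purpose.

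The distortion is 0.25 x (placebo rate minus 744LA rate). Under the stated assumptions, arm differences of 20 to 30 points raise the false rejection rate from 3.8% to between 7.0% and 11.0%. Power for a true 20-point difference falls from 43% to 31% or 15%. With equal rates there is no bias, and with rare events it is slight.

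A reader might go further and conclude that the analysis will show false reassurance, or that the trial's main safety result is affected. Neither follows. The direction depends on an unstated treatment effect. The comparison is a secondary one in a self-selected subset, with use reported at entry or at any later time, so it stays descriptive even when corrected. The primary endpoint does not depend on it.

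**What to change.** Reword (b) so that both sides are limited by arm: women in the 744LA arm who report injectable hormonal contraception versus women in the 744LA arm who do not. Put the same restriction in the sentence that explains (b), and in any output later built on it.

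The cost is one phrase in each of two sentences and no new data. The user group in (b) becomes about 25% smaller (36 instead of 48 in the illustration). If placebo users happened to have the same rate as 744LA users, dropping them would lower power for 70% against 50% from 51% to 43%. That gain from pooling is not usable, because it rests on the two arms having the same rate. The placebo users carry no information on 744LA and remain in comparison (a).

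### Section 9.12 gives comparison (c) two incompatible comparators: an active-arm total that contains the contraceptive users, and a remainder that admits placebo participants

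*SAP*

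**What the plan says.** SAP section 9.12 takes the female participants who "self-report the use of injectable hormonal-based contraception at study entry or at any time during the study period" and compares the proportions meeting a safety or tolerability endpoint in three ways. Comparison (a) is between treatment arms. The second is "b) to the women in the 744LA arm who are do not report use of injectable hormonal contraception". The third is "c) to the overall study population randomized to active GSK1265744".

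The same paragraph then explains the purpose of each. It describes (c) as looking at the users "in contrast to the rest of the enrolled participants in the study". On method it says "All comparisons will be done using the Fisher exact test". The results are to be given by cohort and in aggregate. The section gives no number of users, no alpha and no power for any of the three comparisons. It also does not say whether the user group in (c) is limited to the active arm.

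**The concern.** The two descriptions of (c) name different groups, and neither is a clean comparator.

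- **Defining sentence.** A user randomized to active drug belongs to the population randomized to active drug. She is counted once as a user and again in the total. Fisher's test takes the two rows as separate people, so its p-value does not describe this table.
- **Explanatory sentence.** The remainder excludes the users, so the overlap goes. But the remainder of all enrolled participants includes the placebo arm, although the definition refers to active drug only.

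Two analysts could follow the text faithfully and produce different tables for one prespecified comparison. The analysis serves a listed secondary objective (SAP section 3.2) that has its own endpoint for injectable-contraception users. In a safety comparison, a diluted difference works towards missing an excess of events.

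**Working it through.** The SAP states no figure for (c), so there is none to reproduce. The check has two parts, one for each description.

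**Inputs from the SAP.** Section 2.4 gives "Arm 1: 82 participants received daily oral 744" for Cohort 1 and "Arm 1: Approximately 66 participants will receive daily oral 744" for Cohort 2, so N = 82 + 66 = 148 active participants. It gives 28 + 22 = 50 on placebo. Section 4.1 agrees in round numbers: "approximately 150 in the active drug arm, and 50 in the placebo arm". Section 4.1 expects about 60% women, so active-arm users cannot exceed about 0.60 × 148 ≈ 89.

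**Assumptions, not in the SAP.** Two-sided 0.05; m = 10 to 40 active-arm users; a common event rate of 60% for size; 80% in users against 55% in the others for power.

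**1. Defining sentence (users against a total that contains them).** Let f = m/N be the user share.

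- Observed difference: p_user − [f·p_user + (1 − f)·p_other] = (1 − f)(p_user − p_other). The true difference is multiplied by 1 − f.
- Variance assumed by the test: proportional to 1/m + 1/N, where the disjoint comparison has 1/m + 1/(N − m).
- Approximate ratio of the test statistics: (1 − f)·√{[1/m + 1/(N − m)] / [1/m + 1/N]} = √[(1 − f)/(1 + f)]. For f = 0.2 this is √(0.8/1.2) = 0.82.

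Exact enumeration over two independent binomials (m users and N − m others), with Fisher's test applied to each possible table:

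| Users m | f | True 25-point difference becomes | Size, overlapping | Size, disjoint | Power, overlapping | Power, disjoint |
|---|---|---|---|---|---|---|
| 10 | 0.07 | 23.3 | 0.027 | 0.040 | 25% | 31% |
| 20 | 0.14 | 21.6 | 0.017 | 0.036 | 41% | 53% |
| 30 | 0.20 | 19.9 | 0.012 | 0.037 | 50% | 69% |
| 40 | 0.27 | 18.2 | 0.0075 | 0.038 | 57% | 80% |

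With 5 users power is about 1% against 1.5%, so the comparison is uninformative on either definition.

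By cohort, for 75% in users against 50% in the others:

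- Cohort 1 (82 active, 25 users): power 0.23 overlapping, 0.50 disjoint.
- Cohort 2 (66 active, 20 users): power 0.18 overlapping, 0.40 disjoint.

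A single illustrative table shows the effect. Users 22/30 against others 59/118 gives p = 0.025. Against the overlapping total, (22 + 59)/(30 + 118) = 81/148, it gives p = 0.070.

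**2. Explanatory sentence (users against everyone else enrolled).** Suppose the user row holds only active-arm users. With 20 to 40 of them, the remainder is 148 − 20 + 50 = 178 down to 148 − 40 + 50 = 158 people. Up to 50/178 = 28% to 50/158 = 32% of it is placebo, and less if placebo-arm users are dropped. If active drug adds d points to the event rate and contraception adds nothing, users still exceed this remainder by about 0.28d to 0.32d. For an assumed d of 20 points that is roughly 6 points produced by treatment arm alone. If the user row instead pools users from both arms, the 3:1 allocation puts placebo participants in both rows. That bias then largely goes, but the comparison no longer concerns 744LA recipients.

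**The case against.** **The overlap is only one reading.** A reader might infer from the defining sentence that the overlapping test is the settled plan. The document does not support that, because the explanatory sentence excludes the users. What the text establishes is a contradiction about the comparator. The overlap follows from one side of it and the mixing of arms from the other. This objection stands.

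**The test does not produce false positives.** A reader might infer that a broken independence assumption makes the p-value dangerous in that direction. The enumeration shows the opposite for the overlapping table: true size stays below 0.05 throughout. The harm is conservatism and lost power. This also stands.

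**Other comparisons cover the question.** A reader might infer that a safety signal in contraceptive users would go unseen in the trial. Comparison (b) sets users against active-arm women who do not use injectable contraception. Those groups are disjoint and compare women with women, whereas the rest of the active arm includes men. Comparison (a) covers users across arms. Tables 27 to 29 in section 11.3.1 describe the user subset, and none of their titles names the contrast with the whole active arm. All of this limits the consequence. It does not make (c) analysable as written.

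**The user count is assumed.** This is true, and with few users the loss fades, as the rows for 10 and 5 users show. The contradiction in the text does not depend on the count.

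**Conclusion.** The concern holds as an internal contradiction. Section 9.12 defines (c) against one group and explains it against another, and neither gives active-arm users against the other active-arm participants. The defining sentence yields overlapping rows, a difference reduced by the user share (14% to 27% for 20 to 40 users of 148) and a conservative test that gives up roughly 12 to 23 points of power in the 80% versus 55% scenario. With about 10 users the loss is some 6 points. The explanatory sentence, read literally, puts placebo participants into the comparator. The sizes rest on the assumed user counts, event rates and two-sided 0.05. The primary endpoints are untouched, and the effect is confined to one comparison in a secondary subgroup analysis that has no stated power. It should be corrected, but the trial's safety conclusions do not hang on it.

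**What to change.** In section 9.12, define (c) as active-arm users of injectable hormonal contraception against all other participants randomized to active drug, and reword the explanatory sentence to match. State that the user row in (c) is limited to the active arm. If a comparison with the whole active arm is wanted, show that proportion beside the users' proportion as a description, without a test. Fisher's exact test can stay for the disjoint comparison. The cost is a few words in the SAP, with no new data, procedures or sample size.
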